3. PATIENT SELECTION

3.1 Eligibility Criteria

- 3.1.1 Patients must have histologically or cytologically confirmed *glioblastoma multiforme*, anaplastic astrocytoma, or gliosarcoma.

- 3.1.2 Prior therapy: Patients must have failed external beam radiotherapy to the brain, and if eligible and tolerated, undergone appropriate treatment with temozolomide chemotherapy. All radiation and additional chemotherapies must have been completed at least 4 weeks prior to enrollment. Prior therapy with nitrosoureas must have been completed at least 6 weeks prior to enrollment.
- 3.1.3 Age ≥ 18 years (age of majority for clinical trials in Alabama). Because no dosing or adverse event data are currently available on the use of M032 in patients < 18 years of age, children are excluded from this study but will be eligible for future pediatric phase 1 single-agent trials.
- 3.1.4 Karnofsky Performance Status (KPS) $\geq 70\%$ (see Appendix B).
- 3.1.5 Life expectancy of greater than 4 weeks.
- 3.1.6 Patients must have normal organ and marrow function as defined below:
- leukocytes..... $\geq 3,000/\mu\text{l}$
 - absolute neutrophil count..... $\geq 1,500/\mu\text{l}$
 - platelets..... $\geq 100,000/\mu\text{l}$
 - total bilirubin.....within normal institutional limits
 - AST(SGOT)/ALT(SGPT)..... ≤ 2.5 X institutional upper limit of normal
 - creatinine within normal institutional limits
- OR**
- creatinine clearance..... ≥ 60 mL/min/1.73 m² for patients with creatinine levels above institutional normal.
- 3.1.7 Residual lesion must be ≥ 1.0 cm and ≤ 5.5 cm in diameter without bilateral extension through the corpus callosum as determined by MRI as this is a locally delivered treatment. These parameters will be re-evaluated on imaging done on the day of catheter implantation and if the lesion no longer meets the criteria, the patient will not undergo catheter implantation or treatment with M032.
- 3.1.8 The effects of M032 on the developing human fetus are unknown. For this reason, women of child-bearing potential and men must agree to use adequate contraception prior to study entry and for the first six months after receiving M032. Because it is currently unknown if M032 can be transmitted by sexual contact, a barrier method of birth control must be employed and for six (6) months following the administration of the study drug. Should a woman become pregnant while participating in this study, she should inform her treating physician immediately. For two weeks after receiving M032, subjects should avoid intimate contact with pregnant women, infants and young children and individuals with decreased immunity (ability to fight infection). Subjects should also refrain from donating blood during the trial.
- 3.1.9 Ability to understand and the willingness to sign a written informed consent document.
- 3.1.10 Females of childbearing potential must not be pregnant; this will be confirmed by a negative serum pregnancy test within 14 days prior to starting study treatment.
- 3.1.11 Steroid use is allowed as long as dose has not increased within 2 weeks of scheduled M032 administration. Whenever possible, the patient should be on a steroid dose that is equivalent to a dexamethasone dose of ≤ 2 mg daily at the time of treatment.

3.2 Exclusion Criteria

- 3.2.1 Patients who have had chemotherapy, cytotoxic therapy, immunotherapy within 4 weeks prior to entering the study (6 weeks for nitrosoureas), surgical resection within 4 weeks prior to entering the study, or have received experimental viral therapy or gene therapy at any time (e.g., adenovirus, retrovirus or herpes virus protocol). However, this does not preclude re-treatment with M032 at a later date.
- 3.2.2 Patients who have not recovered from adverse events due to therapeutic interventions administered more than 4 weeks earlier.
- 3.2.3 Patients may not be receiving any other investigational agents.

- 3.2.4 History of allergic reactions attributed to compounds of similar biologic composition to M032 or to IL-12.
- 3.2.5 Tumor involvement which would require ventricular, brainstem, basal ganglia, or posterior fossa inoculation or would require access through a ventricle in order to deliver treatment. Also, since M032 is a local treatment, patients whose tumors have bilateral extension through the corpus callosum, those with actively growing multifocal disease by MRI, and/or CSF dissemination/leptomeningeal disease, are ineligible, .
- 3.2.6 Prior history of encephalitis, multiple sclerosis, or other CNS infection.
- 3.2.7 Required steroid increase within 2 weeks of scheduled M032 administration. When possible, the patient should be on a dexamethasone equivalent dose of ≤ 2 mg daily at the time of treatment.
- 3.2.8 Active herpes lesion.
- 3.2.9 Concurrent therapy with any drug active against HSV (acyclovir, valacyclovir, penciclovir, famcyclovir, gancyclovir, foscarnet, cidofovir).
- 3.2.10 Uncontrolled intercurrent illness including, but not limited to ongoing or active infection, symptomatic congestive heart failure, unstable angina pectoris, cardiac arrhythmia, or any other medical condition that precludes surgery. Also, psychiatric illness/social situations that would limit compliance with study requirements.
- 3.2.11 Excluded patient groups:
- Pregnant women are excluded from this study because M032 is a viral oncolytic therapy with unknown potential for teratogenic or abortifacient effects. Because there is an unknown but potential risk for adverse events in nursing infants secondary to treatment of the mother with M032, breastfeeding women will not be included in the study.
- Because patients with immune deficiency will be unable to mount the anticipated immune response underlying this therapeutic rationale, HIV-seropositive patients are excluded from this study. Other treatment studies for this disease that are less dependent on the patients' immune response are more appropriate for HIV-seropositive patients.
- 3.2.12 Patients with known history of allergic reaction to IV contrast material that is not amenable to pre-treatment by UAB protocol.
- 3.2.13 Patients with pacemakers, ferro-magnetic aneurysm clips, metal infusion pumps, metal or shrapnel fragments or certain types of stents.
- 3.2.14 Receipt of Gliadel Therapy.
- 3.2.15 Receipt of Bevacizumab (Avastin) therapy within 4 weeks of scheduled M032 administration. (Receipt of Bevacizumab (Avastin) greater than 4 weeks of scheduled M032 administration does not exclude patient.
- 3.2.16 Any other reason the investigator deems subject is unfit for participation in the study

3.3 Inclusion of Women and Minorities

Both men and women and members of all ethnic groups are eligible for this trial. The proposed study population, assuming the maximum number of patient enrollments occurs, is illustrated in the table below.

Gender	Asian or Pacific Islander American Indian or Alaskan Native	*Black, not of Hispanic Origin	Hispanic	White, not of Hispanic Origin	Other or Unknown (Non-white)	*Total
Female	--	1	1	8	--	10
Male	--	1	0	9	--	10
TOTAL	--	2	1	17	--	20

*Based on percentages of patients with recurrent malignant gliomas treated at UAB 2000-2015

4. TREATMENT PLAN

4.1 Study Summary

This will be an open-label, CRM-directed, dose-escalating Phase I safety trial conducted at a single site (UAB) in patients with a confirmed diagnosis of progressing MG after TMZ chemoradiation therapy. Treatment will be administered on an inpatient basis. Expected adverse events caused by M032 are described in **Section 5**. No investigational or commercial agents or therapies other than those described below may be administered with the intent to treat the patient’s malignancy.

These subjects will include eligible patients for whom surgical resection of their recurrent glioma is considered to be infeasible or would not likely afford greater benefit than the potential risks associated with surgical resection. All patients will be required to be placed on an anticonvulsant at the time of screening; those patients already on an anti-convulsant (anti-epileptic drug/AED) will have a second anti-convulsant added per the discretion of the investigator. This anti-convulsant will be continued for a minimum of 28 days unless the patient develops a reaction to the medication. If this develops, all attempts will be made to implement an alternative agent. On Day 0, these subjects will be treated under monitored local anesthesia, or at the surgeon’s discretion, under general anesthesia. The patients will undergo a contrasted MRI scan to determine the site(s) for stereotactic biopsy and inoculation of the test agent. Patients will then undergo stereotactic biopsy of their tumor. While evidence of radiation damage or necrosis may be present on the frozen section, inoculation with M032 will only proceed if viable, recurrent glioma is also present on the frozen section.

These patients will undergo placement of one to four stereotactically placed catheters, which will be primed in the OR with 0.4 ml preservative-free normal sterile saline solution per catheter. The wound will be closed, the catheters aseptically exteriorized and the subject allowed to recover overnight from the procedure in the Neurosurgery ICU. If the patient’s condition is stable they may be transferred the next morning, Day 1, to a Clinical Research Unit bed for M032 administration and monitoring until discharge. After pathology results confirm recurrent tumor, and a CT confirms appropriateness of catheter placement, infusion of M032 may begin. If a catheter is determined, by the investigator, to be out-of-position and cannot be properly positioned by simple partial withdrawal at the bedside (as determined by the surgeon investigator), this/these catheter(s) will not be used for infusion. The catheters will be removed 6-18 hours after the completion of the infusion.

Patients will then receive the entire M032 dose by intratumoral infusion over a 6 hour period (infusion may extend up to 12 hours, if needed due to catheter malfunction). The total amount of M032, as defined by each patient’s dose level, will be delivered in a total volume of ~2.4 ml administered in up to four catheters, each attached to a separate syringe mounted in an approved syringe pump for a total infusion rate of 400 microliters (0.4 ml) per hour. However, the infusion of the first syringe(s) will actually last 3 hours and 35 minutes to allow flushing of the saline solution from the catheter(s). The infusion rate for the flush will be 400 microliters (0.4 ml) per hour for 35 minutes per catheter. After the 35 minute flush, the infusion rate will be changed to the appropriate rate for the M032 infusion. Subsequent to this, the rate of administration through each individual catheter shall be determined by the equation:

400 microliters (0.4 ml) per hour/number of active catheters.

Each catheter will be placed in a different enhancing area of the tumor and labelled. If, in the surgeon’s judgment, the tumor location or other properties are not suitable for all four catheters to be placed, fewer catheters will be placed, ranging from number one to four.

The total volume administered from each syringe will be determined by the number of catheters actively infusing, using a volume of 400 microliters (0.4 ml) per hour as a guide. Each initial loaded syringe will be replaced at 3 hours 35 minutes after the infusion is started with a new loaded syringe that has been maintained at 4°C and new infusion tubing. Refer to table below.

Table : Plan for Loading rate and Infusion Rate for M032 HSV		
Number of Catheters	Initial Loading Rate for First 35 mins per catheter	Final Infusion Rate per catheter
1	0.4 cc/hour	0.4cc/hour

2	0.4 cc/hour	0.2cc/hour
3	0.4 cc/hour	0.13 cc/hour
4	0.4 cc/hour	0.1cc/hour

For each of the study drug infusion periods [active catheter(s)/pump(s)], the study drug syringe will be connected to the infusion tubing, that has been flushed with sterile PBS + 10% glycerol (Alanza) . The infusion tubing will then be primed with 4.6 ml of the diluted M032 virus preparation in the syringe and connected to the catheter. The first infusion period will begin with a 35 minute flush of the saline solution from the catheter at a rate of 0.4ml/hour/catheter. After completion of the flush, the pump will be reprogramed to the appropriate rate for the study drug infusion and the infusion begun. After the first period of infusion is complete, the infusion of the study drug from a single syringe at 400 microliters/hour should be 1.2ml. The infusion will be stopped, and the above procedure (minus the flush) repeated for the second syringe that has been stored at 4°C and new infusion tubing. After two infusion periods, the delivery of the total planned dose should be complete.

If delivery at the desired rate is not possible through an individual catheter, the rate of delivery through that catheter may be slowed and the rate of delivery through the remaining catheters increased as possible to attempt to maintain total delivery rate at 400 microliters (0.4 ml) per hour.

After the initiation of the infusion, the subjects' vital signs (temperature, blood pressure, pulse, respiratory rate) and neurologic function and limited neurological exam will be monitored every hour for the first twelve hours, then every two hours for the next 12 hours, then every 4 hours for the next 24 hours. Thereafter, the frequency of monitoring will be determined by the attending physician(s) based on the medical condition of the patient.

After discharge the subject will continue to be closely followed for evidence of adverse events, with outpatient follow-up evaluations scheduled at Day 10 and months 1, 2, 3, 4, 5, 6, 9 and 12, or more often if medically indicated. HSV detection will be performed at additional time points. The visits at months 2, 4 and 5 will consist of sample collections and a study coordinator visit only. Due to the complicated procedure for obtaining samples remotely at visits 2, 4 and 5, if a patient is unable to travel then, and if determined feasible by the PI, an attempt can be made to have the specimens collected by the patients' referring physician and sent to UAB for analysis.

4.1.1 Continual Reassessment Method

[name] and [name], Professors in the Department of Biostatistics, UAB School of Public Health, with expertise in CRM calculations will apply the software developed by [name], (Cedars-Sinai) who will serve as a clinical trial statistical consultant to advise and assist in the implementation of the Continual Reassessment Method in determining dose alterations. In addition, Drs. [name] and [name], will provide support in clinical trial and data management, and data analysis.

Rationale for the Use of a Modified Continual Reassessment Method: The description of the determination of MTD from the CRM that we are employing is adapted from that used previously in a Phase I/II study of the poly (ADP-ribose) polymerase-1 (PARP-1) inhibitor BSI-201 in patients with newly diagnosed malignant glioma conducted under the New Approaches to Brain Tumor Therapy (NABTT) CNS Consortium. To estimate the MTDs in terms of clinical toxicities, a modified continual reassessment method (CRM), based on that described by Piantadosi et al [45], will be employed. The CRM has been shown to be less biased and more efficient for estimating the MTD than traditional dose-finding models. The efficiency of the CRM stems from its explicit use of biological knowledge in the form of a parametric dose toxicity model. In the CRM, only a starting dose is specified and the dose is escalated or deescalated based on the toxicities of the previous cohort.

This is advantageous because the investigators can choose the next dose level based on all available clinical and statistical information rather than on relatively arbitrary predetermined doses. One disadvantage of the CRM is uncertainty of the dose levels that will be used in the trials, because the specific dose levels are not defined at the start of the trial.

Details of CRM Design: The primary statistical outcome for this study is the occurrence of serious clinical toxicity. Investigators would like to employ a dose of drug that yields approximately a 1/3 chance of serious toxicity. In our opinion, this represents the best chance at a beneficial therapeutic ratio for this unusually difficult disease to treat. This target probability of toxicity is chosen based on knowledge of previous trials of oHSV in

glioma, but is fundamentally subjective. The relationship between dose of drug and probability of toxicity is assumed to follow a two-parameter logistic model, both before and during the dose finding given by:

$$P(\text{toxicity}|\text{dose}) = \frac{1}{1 + e^{-\beta(\text{dose}-d_{50})}}$$

where β is the “slope” of the curve and d_{50} the midpoint (or dose that yields a 50% response). The parameters β and d_{50} govern the dose finding process, and are estimated, denoted by $\hat{\beta}$ and \hat{d}_{50} , initially by clinical judgment and afterwards by the observed data. This represents a second subjective component of dose finding designs.

Classical dose-ranging designs incorporate this component of subjectivity by setting out, in advance of the experiment, a set of doses to employ. A strictly Bayesian approach to the CRM requires a joint prior probability distribution for the parameters β and d_{50} . However, we have found it easier for clinicians to render their clinical judgment about β and d_{50} in the form of pseudo-data. Specifically, we ask for two points on the dose toxicity curve: the dose thought to yield a 10% probability of toxicity (d_{10}) and the dose thought to yield a 90% probability of toxicity (d_{90}). Two points, d_{10} , d_{90} , are required to initiate the fit for a two-parameter model. The exact points chosen are arbitrary, but we have found these generally work well or are easily adapted. The d_{10} point can often be discarded after some data have been obtained. The d_{90} point is necessary to obtain a fit of the model, but is usually relatively unimportant because it characterizes a region of the model that does not heavily influence prediction of the next dose. In this sense, d_{90} is a nuisance parameter – necessary for model fitting, but relatively uninfluential on the dose escalation.

At both d_{10} and d_{90} , the investigator specifies a numerator (number of responses) and denominator (number of subjects treated), such that numerator/denominator = 0.1 or 0.9 as the case may be. The denominators are always taken to be small numbers, e.g. 1, to represent weak evidence and reduce the influence of these points compared to real subject data.

Three values for d_{90} will be chosen in this protocol with weights of one tenth that of real subject data. This allows flexibility in the upper end of the dose toxicity curve. This adaptation to the CRM came about after subject data demonstrated that d_{90} was incorrect in previous studies, because doses approaching d_{90} were tried with no toxicities observed. This situation required that d_{90} be moved to a higher dose or the fitted dose toxicity curve became too steep and no dose escalations resulted.

We assume the dose for $d_{10} = 1 \times 10^4$ pfu for M032 (**Table 1**). A set of three values will be chosen for $d_{90} = 1 \times 10^{15}$ pfu. These values for d_{90} spread probability mass over a wider range and may eliminate the need to increase d_{90} if the data are inconsistent with a single value. Based on these starting points, our desire is to employ a dose of virus to yield no more than 33% chance of clinical toxicity. The initial starting dose will be assumed to be 1×10^5 PFU and the maximum dose to be tested would be 1×10^9 PFU. Further assumptions would be that the maximum number of subjects would be 204 and that the dose cohort size would be 1. Further, the next CRM recommended log dose would be rounded to the nearest 0.5 or full dose. Moreover, the number of consecutive subjects at the maximum tolerated dose would be 10 or a number until 20 subjects are treated, whichever comes first. This will allow us to collect more information of the safety of the MTD. If a second toxicity is observed for patients on the highest dose, then the next lower dose is used and declared MTD if 10 consecutive subjects on the same dose are toxicity free or if n=20 is reached. If more toxicities are found, CRM will be used in the de-escalation of the dose.

The outcome space for the first CRM iterations would look like the values shown as six sample scenarios in **Table 2** using a starting dose 1×10^5 pfu. We will not allow dose escalations to exceed 10 times the maximum dose already administered. In this way, we prevent a too rapid dose escalation or testing high doses without a reasonable degree of certainty concerning their safety. Although the values in **Table 2** appear reasonable to us currently, we emphasize that they should not be taken literally. Indeed, if we receive approvals (DSMB, IRB, FDA), we will update the CRM model using the four patients previously enrolled and treated. Some of the data

Table 1: Initializing Data used to start the CRM			
Log Dose	N	r	Weight
4	1	0.05	0.5
5	1	0.10	0.5
6	1	0.2	0.5
7.5	1	0.5	0.5
9	1	0.8	0.5
10	1	0.9	0.5
12	1	1	0.5
15	1	1	0.5

(Initial recommended dose based on these data=6.7842)

$$L(\beta, d_{50}) = \sum_{i=1}^k \left[\log \binom{n_i}{r_i} - n_i \log(1 + e^{-\beta(d_i - d_{50})}) - (n_i - r_i) \log(1 + e^{-\beta(d_i - d_{50})}) \right]$$

could suggest that the current value for d_{10} and/or d_{90} is inappropriate. We would not proceed blindly with a CRM (or any other) dose escalation in such a circumstance. All testing doses will be the estimated dose round-down to the nearest 10th.

For each subsequent level, the investigators will evaluate the recommended dose-level. It is possible that the model may recommend large interval increases in dose level with which the investigators do not feel comfortable. In these cases, the investigators will use this information and their best clinical judgment to assign a next dose level. We emphasize that the dose levels recommended by the CRM should not be taken literally.

Model based dose escalation methods, especially the CRM, are able to account for ordinal or quantitative toxicity assessments, and use this information to guide subsequent dose changes. In particular, the binomial likelihood is

where i indexes the dose level, p is the probability of toxicity (equation 1 above), d is dose, n the number of subjects treated at each dose, and r the number of toxicities. While n is constrained to be an integer, r does not have to be integral. In particular, r can be taken to be the sum of ordinal or quantitative toxicity measures provided that $r < n$. The maximization of equation 2 with respect to the parameters (model fitting) can then proceed in the usual fashion. Furthermore, the ordinal scores need not be the same for all types of toxicity. For example, we might not want alopecia to have the same effect on dose reduction as neurologic toxicities.

Table 2: Six Different CRM-defined Dose Escalation Scenarios

Subject #	S1	S2	S3	S4	S5	S6
1	5	5	5	5	5	5
2	6	6	6	6	6	6
3	7	7	7	7	7	7
4	7.5	7.5	7.5	7.5	7.5	7.5
5	8	8	8	8	8	8
6	8	8	8	8	8	8
7	8.5	8.5	8.5	8.5	8.5	7.5
8	9	9	9	9	8	8
9	9	8.5	9	9	8.5	8
10	9	8.5	9	9	8.5	8
11	9	8.5	9	8	8.5	8.5
12	9	8.5	9	8.5	9	8.5
14	9	8.5	9	8.5	9	9
15	9	8.5	9	8.5	9	9
16	9	8.5	9	8.5	9	9
17	9	8.5	8.5	8.5	9	9
18	9	8.5	8.5	8.5	9	9
19		8.5	8.5	8.5	9	9
20			8.5	8.5	9	9
MTD	9	8.5	8.5	8.5	9	9

(yellow cells= maximum tolerated dose (MTD); magenta cells =toxicity; white cells=no toxicity)

As subjects are treated at doses estimating the true MTD, the recommended subsequent dose levels will begin to converge. The criteria to declare the MTD will be when 2 recommended doses are within 10% of one another. It is possible that the dose escalation could continue indefinitely and that the MTD is not reached. If 10 subjects are treated in the full dose range in this dose-finding study and the MTD has not been reached, we will take pause, evaluate the data in consultation with the DSMB, and determine whether to continue the dose-escalation or terminate the Phase I portion of the study. If a MTD is not being reached based on clinical toxicities (too many or too few), the biological indicator (increased PFS or OS) may factor in the choice of the M032 dose for the ultimate planned phase II trial.

A maximum of 10 subjects will be treated at the putative MTD to have better estimation of $\leq 33\%$ DLT rate.

No enrollment of special or vulnerable populations is anticipated.

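### Section 4.1.1 gives two incompatible sets of CRM start-up data and two conflicting rounding rules, and the stated initial recommendation of 6.7842 does not reproduce from Table 1

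*Combined protocol and SAP*

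**What the plan says.** All of this is in Section 4.1.1 of the combined protocol and SAP.

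- **Model and target.** Toxicity "is assumed to follow a two-parameter logistic model, both before and during the dose finding". The target appears as "Investigators would like to employ a dose of drug that yields approximately a 1/3 chance of serious toxicity" and as "our desire is to employ a dose of virus to yield no more than 33% chance of clinical toxicity".
- **Start-up data in the text.** d10 is 10^4 pfu, with a pointer to Table 1. Three d90 values are announced to spread the upper end of the curve, but only 10^15 pfu is printed. The d90 values "will be chosen in this protocol with weights of one tenth that of real subject data". No weight is given for d10. By definition the pseudo-data ratio is 0.1 at d10 and 0.9 at d90.
- **Start-up data in Table 1**, titled "Initializing Data used to start the CRM". Log dose and r (N = 1 in each row): 4, 0.05; 5, 0.10; 6, 0.2; 7.5, 0.5; 9, 0.8; 10, 0.9; 12, 1; 15, 1. Every row has weight 0.5. The note beneath reads "Initial recommended dose based on these data=6.7842".
- **Rounding.** One paragraph says "the next CRM recommended log dose would be rounded to the nearest 0.5 or full dose". A later one says "All testing doses will be the estimated dose round-down to the nearest 10th".
- **Limits.** The starting dose is 10^5 PFU, the maximum is 10^9 PFU, and no step may exceed ten times the highest dose already given.

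**The concern.** The synopsis makes the CRM-estimated highest safe dose the primary endpoint. In a small trial that assigns one subject at a time, the pseudo-data, their weight and the rounding rule shape each model recommendation. Table 1 carries 8 × 0.5 = 4 patient-equivalents, against at most 20 further subjects (24 in total, Section 4.1.2).

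A DSMB, IRB or FDA reader cannot tell from Section 4.1.1 which model will run. If the printed inputs do not give the printed output, then the table, the target or the fitting method differs from what is described. The two descriptions could also escalate at different speeds.

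**Working it through.** **1. The two sets side by side (log10 dose)**

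| Item | Text | Table 1 |
|---|---|---|
| 10% point | 4 | 5 (log dose 4 carries 5%) |
| 90% point | three values announced, only 15 printed | 10 only (12 and 15 carry 100%) |
| Weight | 0.1 for the d90 points; d10 not stated | 0.5 for all eight rows |

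Table 1 also has r = n at log doses 12 and 15, although the section requires r to be smaller than n.

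**2. The plan's own figure, 6.7842**

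I maximised the sum of w[r log p + (n − r) log(1 − p)] with p = 1/(1 + e^(−β(d − d50))) over the eight rows. The fit is β = 0.9195, d50 = 7.461. A weight common to all rows cancels, so 0.5 or 1 gives the same answer. The recommended log dose is d50 + logit(target)/β:

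- target 0.33: 7.461 − 0.708/0.9195 = 6.691
- target 1/3: 7.461 − 0.693/0.9195 = 6.707

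In PFU, 10^6.7842 is 6.08 million against 4.91 and 5.10 million, a ratio of 1.24 or 1.19. On the half-log rule 6.7842 rounds to 7.0, while 6.691 and 6.707 both round to 6.5. Other fitting methods gave 6.71–6.73 (non-linear least squares), 6.67–6.68 (least squares on log-odds), 6.62–6.63 (probit) and 6.80 (flat-prior Bayesian plug-in at weight 0.5). Dropping rows gets a few arbitrary subsets within about 0.0005, but none gives 6.7842.

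**3. Start-up recommendation from the text's points**

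The missing values have to be assumed.

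- *All three d90 values at 15.* The curve passes through both points: β = 2 × 2.197/(15 − 4) = 0.3995, d50 = 9.5, d33 = 9.5 − 0.708/0.3995 = 7.73, whatever the d10 weight.
- *d90 at 10, 12 and 15, weight 0.1 each.* d33 = 5.99, 6.54 or 6.62 for a d10 weight of 0.1, 0.5 or 1.

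The range is therefore about 6.0 to 7.7, on either side of Table 1's 6.69.

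**4. Escalation with no DLTs** (start 5, half-log rounding, ten-fold cap, ceiling 9, target 0.33; the arrival subjects are the same at 1/3)

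| Start-up data | Doses by subject | First at 9 |
|---|---|---|
| Table 1, weight 0.5 | 5, 6, 7, 7.5, 8, 8.5, 8.5, 9 | subject 8 |
| Table 1, weight 0.1 on rows 10, 12 and 15 only | 5, 6, 7, 7.5, 8, 8.5, 9 | subject 7 |
| Text points, d90 all 15 or 10/12/15, d10 weight 0.1, 0.5 or 1 | 5, 6, 7, 8, 9 | subject 5 |

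In the last row every model recommendation lies above what the cap or ceiling allows. The lowest recommendations for subjects 2 to 5 are 7.82, 8.66, 9.36 and 9.80, against limits of 6, 7, 8 and 9. The cap and ceiling alone set the dose.

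Table 2 scenarios 1 to 4 also first show 9 at subject 8. They show 8 at subject 6, where the Table 1 fit recommends 8.31, which rounds to 8.5, so the match is on arrival only. Table 2's toxicity colours are not readable in the text available, so it could not be checked further.

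**5. Rounding**

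I read the tenth as a tenth of a log. Table 1 at weight 0.5 would then give 7.6 and 7.9 for subjects 4 and 5. Table 2 has 7.5 and 8 there and uses whole and half logs throughout.

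**6. Printed log-likelihood**

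Both variable terms contain log(1 + e^(−β(d − d50))), multiplied by n and by (n − r), and no weight appears. At β = 1 with Table 1's rows and without the constant, it equals −16.2 at d50 = 7.5, −4.6 at 5, −0.05 at 0 and −2.5 × 10^−6 at −10. It rises toward 0 without reaching it, so it has no finite maximiser. Replacing the second term by (n − r)β(d − d50) restores the binomial form.

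**The case against.** Several points on the other side are sound.

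- **6.7842 is not a dose given.** The start is fixed at 10^5 PFU, and the ten-fold cap sets subjects 2 and 3 under every version run. The gap is under 0.1 log and the software's fitting method is not described. The figure works only as a consistency check, but a fit printed to four decimals should reproduce from its own table.
- **The CRM does not act alone.** Investigators may depart from a recommendation, the Medical Monitor and DSMB review each dose step (Section 4.2), and the model may be re-seeded with four treated patients if approved. So these inputs do not fix every assignment. They still enter every fit, and the caution against literal reading does not reconcile two input sets.
- **The likelihood may be misprinted or misread.** The equation is detached from its lead-in in the text available, and the section calls it binomial.

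A reader might also infer more than the documents support:

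- *That the real target is about 35%.* On the Table 1 curve 6.7842 is the 34.9% dose. But a 0.349 target brings 10^9 forward to subject 7, which fits Table 2 less well. The figure is unreproduced; the cause is unknown.
- *That the text implies a start-up d33 of 10^7.73.* This needs three identical d90 values, which sits badly with the aim of spreading them. With 10/12/15 the figure falls below Table 1's.
- *That one tenth applies to all of Table 1.* The text gives that weight to the d90 points only; that change alone moves arrival from subject 8 to subject 7.
- *That no model can be fitted.* The printed expression is bounded by 0, and existing CRM software does the fitting.

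**Conclusion.** The point holds. The text and Table 1 contradict each other on the 10% dose, the 90% dose and the weight, and the two rounding sentences are incompatible. These contradictions stand without any calculation. The stated 6.7842 does not follow from Table 1 at either wording of the target: the binomial fit gives 6.69 or 6.71.

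The practical size is a shift in first arrival at 10^9, with no DLTs and half-log rounding, from subject 8 (Table 1) to subject 5 (text points). The subject-5 result rests on assumptions about the two unprinted d90 values and the d10 weight, and held for each combination in the table. The start-up d33 under the text is uncertain, about 10^6.0 to 10^7.7, so no single contrast with Table 1 should be quoted. The likelihood is an item to check, not an established fault in the software. Nothing here shows that any subject was wrongly dosed or which version is right.

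**What to change.** Before the next dose assignment, amend Section 4.1.1 as follows:

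1. Reconcile the text and Table 1 to one set of pseudo-data. State every dose, ratio and weight, including all three d90 values and the d10 weight, and resolve r = n against the r < n condition.
2. Keep one rounding rule, and say whether it applies to the log dose.
3. Check the printed likelihood against the software and print the weighted binomial form: the sum of w[log C(n, r) − r log(1 + e^(−β(d − d50))) − (n − r) log(1 + e^(β(d − d50)))].
4. Refit, name the fitting method, and restate the initial recommendation at one stated target.
5. Regenerate Table 2 from the same inputs, with toxicities marked in text as well as colour.

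Which inputs and rule to keep is for the sponsor, its statisticians and the DSMB; this review proposes no dose. The cost is amendment wording and a rerun of the existing CRM software.
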